16 DATA COLLECTION, RETENTION AND MONITORING

16.1 Data Collection Instruments

The Investigator will prepare and maintain adequate and accurate source documents designed to record all observations and other pertinent data for each subject treated with the study drug.

Study personnel at each site will enter data from source documents corresponding to a subject's visit into the protocol-specific Case Report Form (eCRF) when the information corresponding to that visit is available. Subjects will not be identified by name in the study database or on any study documents to be collected, but will be identified by a site number, subject number and initials.

If a correction is made on a CRF, the study staff member will line through the incorrect data, write in the correct data and initial and date the change.

The Investigator is responsible for all information collected on subjects enrolled in this study. All data collected during the course of this study must be reviewed and verified for completeness and accuracy by the Investigator. A copy of the CRF will remain at the Investigator's site at the completion of the study.

16.2 Data Management Procedures

The data will be entered into a validated database. The Data Management group will be responsible for data processing, in accordance with procedural documentation. Database lock will occur once quality assurance procedures have been completed.

All procedures for the handling and analysis of data will be conducted using good computing practices meeting FDA guidelines for the handling and analysis of data for clinical trials.

16.3 Data Quality Control and Reporting

After data have been entered into the study database, a system of computerized data validation checks will be implemented and applied to the database on a regular basis. Query reports (Data Clarification Requests) pertaining to data omissions and discrepancies will be forwarded to the Investigators and study monitors for resolution. The study database will be updated in accordance with the resolved queries. All changes to the study database will be documented.

16.4 Archival of Data

The database is safeguarded against unauthorized access by established security procedures; appropriate backup copies of the database and related software files will be maintained. Databases are backed up by the database administrator in conjunction with any updates or changes to the database.

At critical junctures of the protocol (e.g., production of interim reports and final reports), data for analysis is locked and cleaned per established procedures.

16.5 Availability and Retention of Investigational Records

The Investigator must make study data accessible to the monitor, other authorized representatives of the Sponsor (or designee), IRB, and Regulatory Agency (e.g., FDA) inspectors upon request. A file for each subject must be maintained that includes the signed Informed Consent, HIPAA Authorization and copies of all source documentation related to that subject. The Investigator must ensure the reliability and availability of source documents from which the information on the CRF was derived.

All study documents (patient files, signed informed consent forms, copies of CRFs, Study File Notebook, etc.) must be kept secured for a period of two years following marketing of the investigational product or for two years after centers have been notified that the IND has been discontinued.

16.6 Subject Confidentiality

In order to maintain subject confidentiality, only a site number, subject number and subject initials will identify all study subjects on CRFs and other documentation. Additional subject confidentiality issues (if applicable) are covered in the Clinical Study Agreement.

17 ADMINISTRATIVE, ETHICAL, REGULATORY CONSIDERATIONS

The study will be conducted according to the Declaration of Helsinki, Protection of Human Volunteers (21 CFR 50), Institutional Review Boards (21 CFR 56), and Obligations of Clinical Investigators (21 CFR 312).

To maintain confidentiality, all laboratory specimens, evaluation forms, reports and other records will be identified by a coded number and initials only. All study records will be kept in a locked file cabinet and code sheets linking a patient's name to a patient identification number will be stored separately in another locked file cabinet. Clinical information will not be released without written permission of the subject, except as necessary for monitoring by the FDA. The Investigator must also comply with all applicable privacy regulations (e.g., Health Insurance Portability and Accountability Act of 1996, EU Data Protection Directive 95/46/EC).

17.1 Protocol Amendments

Any amendment to the protocol will be written by the investigator. Protocol amendments cannot be implemented without prior written IRB/IEC approval except as necessary to eliminate immediate safety hazards to patients. A protocol amendment intended to eliminate an apparent immediate hazard to patients may be implemented immediately, provided the IRBs are notified within five working days.

17.2 Institutional Review Boards

The protocol and consent form will be reviewed and approved by the IRB prior to study initiation. Serious adverse events regardless of causality will be reported to the IRB in accordance with the standard operating procedures and policies of the IRB, and the Investigator will keep the IRB informed as to the progress of the study. The Investigator will obtain assurance of IRB compliance with regulations.

Any documents that the IRB may need to fulfill its responsibilities (such as protocol, protocol amendments, Investigator's Brochure, consent forms, information concerning patient recruitment, payment or compensation procedures, or other pertinent information) will be submitted to the IRB. The IRBs written unconditional approval of the study protocol and the informed consent form will be in the possession of the Investigator before the study is initiated. The IRBs unconditional approval statement will be transmitted by the Investigator to Sun Pharmaceutical Industries Ltd, prior to the shipment of study supplies to the site. This approval must refer to the study by exact protocol title and number and should identify the documents reviewed and the date of review.

Protocol and/or informed consent modifications or changes may not be initiated without prior written IRB approval except when necessary to eliminate immediate hazards to the

patients or when the change(s) involves only logistical or administrative aspects of the study. Such modifications will be submitted to the IRB and written verification that the modification was submitted and subsequently approved should be obtained.

The IRB must be informed of revisions to other documents originally submitted for review; serious and/or unexpected adverse events occurring during the study in accordance with the standard operating procedures and policies of the IRB; new information that may affect adversely the safety of the patients of the conduct of the study; an annual update and/or request for re-approval; and when the study has been completed.

17.3 Informed Consent Form

Informed consent will be obtained in accordance with the Declaration of Helsinki, ICH GCP, US Code of Federal Regulations for Protection of Human Subjects (21 CFR 50.25[a,b], CFR 50.27, and CFR Part 56, Subpart A), the Health Insurance Portability and Accountability Act (HIPAA), and local regulations.

The Investigator will prepare the informed consent form, assent and HIPAA authorization and submit to the IRB. The consent form generated by the Investigator must be acceptable and be approved by the IRB. The written consent document will embody the elements of informed consent as described in the International Conference on Harmonisation and will also comply with local regulations.

A properly executed, written, informed consent will be obtained from each subject prior to entering the subject into the trial. Information should be given in both oral and written form and subjects (or their legal representatives) must be given ample opportunity to inquire about details of the study. If a subject is unable to sign the informed consent form (ICF) and the HIPAA authorization, a legal representative may sign for the subject. A copy of the signed consent form will be given to the subject or legal representative of the subject and the original will be maintained with the subject's records.

17.4 Publications

The publication or presentation of any study results shall comply with all applicable privacy laws, including, but not limited to, the Health Insurance Portability and Accountability Act of 1996.

17.5 Investigator Responsibilities

By signing the Agreement of Investigator form, the Investigator agrees to:

[figure not shown]
1. Conduct the study in accordance with the protocol, except when to protect the safety, rights or welfare of subjects.
2. Personally conduct or supervise the study (or investigation).
3. Ensure that the requirements relating to obtaining informed consent and IRB review and approval meet federal guidelines, as stated in § 21 CFR, parts 50 and 56.
4. Report to the Sponsor or designee any AEs that occur in the course of the study, in accordance with §21 CFR 312.64.

5. Ensure that all associates, colleagues and employees assisting in the conduct of the study are informed about their obligations in meeting the above commitments.
6. Maintain adequate and accurate records in accordance with §21 CFR 312.62 and to make those records available for inspection with the Sponsor (or designee).
7. Ensure that an IRB that complies with the requirements of §21 CFR part 56 will be responsible for initial and continuing review and approval of the clinical study.
8. Promptly report to the IRB all changes in the research activity and all unanticipated problems involving risks to subjects or others (to include amendments and IND safety reports).
9. Seek IRB approval before any changes are made in the research study, except when necessary to eliminate hazards to the patients/subjects.
10. Comply with all other requirements regarding the obligations of clinical investigators and all other pertinent requirements listed in § 21 CFR part 312.

APPENDIX I. SCHEDULE OF STUDY VISITS

	Screening (Day -29 to Day 1)	Day 1 (may be combined with screening)	Day 3 (telephone)	Day 8	Day 15 (telephone)	Day 29	Day 84
Informed consent	X						
Medical history	X						
Concomitant medications	X	X		X		X	X
Adverse events		X	X	X	X	X	X
Urine Pregnancy test (if applicable)	X						
Randomization		X					
ALA-PDT		X					
AK count	X	X		X		X	X
AE assessment		X	X	X	X	X	X
Local Skin Reaction		X (pre and post)		X		X	X
Symptom Assessment		X	X	X	X	X	X
Skindex-16		X	X	X	X	X	X
Photography		X		X		X	X

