6.2 Inclusion Criteria

- Adults at least 18 years old.
- Subjects must be able to read, sign, and understand the informed consent
- Subjects have at least 4 and no more than 20 clinically typical, visible actinic keratoses in the target treatment area on the face or scalp.
- Subject must be willing to forego any other treatments for AK in the treatment area on the face or scalp, during the study period, and for 14 days prior to enrollment; including cryotherapy, topical 5-fluorouracil, imiquimod, and ingenol mebutate.
- Subjects who have previously received PDT must undergo at least an 8-week washout period prior to enrollment in study.
- Subject must be willing and able to participate in the study and to comply with all study requirements including concomitant medication and other treatment restrictions, and telephone interview.
- If subject is a female of childbearing potential she must have a negative urine pregnancy test result prior to study treatment initiation and must agree to use an approved method of birth control while enrolled in the study. Women who are pregnant, lactating, or planning to become pregnant during the study period are excluded from the study.

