9.1.5 Vital Signs

Body temperature, blood pressure, pulse and respirations will be performed after resting for 5 minutes at Screening and at day 1.

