9.2 Clinical Laboratory Measurements

9.2.1 Pregnancy Test

A urine pregnancy test will be obtained from female subjects who are of childbearing age prior to their participation in the study.

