10.1 Visit 1 (Screening, Day -29 to 1)

1. Review the study with the subject (or subject's legal representative) and obtain written informed consent and HIPAA authorization.
2. Assign the subject a unique screening number.

3. Record demographics data.
4. Record medical history, including a history of actinic keratosis, diagnosis date, and prior AK treatments.
5. Record concomitant medications.
6. Perform a complete physical examination.
7. Perform and record vital signs.
8. Perform urine pregnancy test in female subjects of childbearing age.
9. Obtain informed consent.
10. Photography of treatment area.
11. Schedule subject for visit 2 in 0-29 days.

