10.2 Visit 2 (Day 1, may be combined with Screening)

Unblinded investigator:

1. Randomization to treatment arms (1:1:1). Investigator will use sequential envelopes with randomly prefilled treatment arms. Envelopes will be filled in batches of three (nine patients) to ensure even allocation between arms during the course of treatment.
2. Perform and record vital signs.
3. Concomitant medications and Adverse Events review.

Blinded investigator:

4. Perform abbreviated physical examination.
5. Perform an AK count
6. Perform a pre-treatment local skin response assessment
7. Curette any hypertrophic AK
8. Application of ALA

Unblinded investigator:

9. Monitor ALA incubation duration depending on treatment arm
10. Light exposure (BLU-U and/or sunlight, depending on treatment arm)
11. Symptom assessment. All subjects will have symptom assessments at 15, 30, 45, 60, and 75 minutes (Table 2).
12. Skindex-16
13. Record any Adverse Events.
14. Photography of treatment area.

Blinded investigator:

15. Perform a post-treatment local skin response assessment

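### When Screening and Day 1 are separate visits, the only scheduled pregnancy test can be up to 29 days old when ALA is applied, and none is scheduled on Day 1

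*Combined protocol and SAP*

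**What the plan says.** For a woman of childbearing potential, the inclusion criterion in 6.2 sets two conditions. The first concerns testing: "she must have a negative urine pregnancy test result prior to study treatment initiation". The second concerns contraception; each such woman "must agree to use an approved method of birth control while enrolled in the study". The same bullet excludes women who are pregnant, lactating or planning a pregnancy during the study. It gives no maximum age for the negative result.

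The test itself appears in three places:

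- Section 9.2.1: "A urine pregnancy test will be obtained from female subjects who are of childbearing age prior to their participation in the study". No repeat is mentioned.
- Section 10.1, item 8 of the Screening visit: "Perform urine pregnancy test in female subjects of childbearing age".
- Appendix I: the row "Urine Pregnancy test (if applicable" has one mark, in the Screening column.

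Section 10.1, item 11 sets the gap to the treatment visit: "Schedule subject for visit 2 in 0-29 days". Section 10.2 opens with "Randomization to treatment arms (1:1:1" and places ALA application at step 8 of 15. No step is a pregnancy test. Section 10.2 and Appendix I allow Screening and Day 1 to be the same visit, but do not require it.

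**The concern.** ALA is applied once, on Day 1 (8.4.1). A test just before that application is the last one that can prevent the exposure 6.2 is meant to rule out. When the visits are separate, the protocol relies on a result from Screening and does not check again.

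Section 12.1 lists a positive pregnancy test among the reasons for stopping treatment, but no scheduled test can trigger that rule. A positive result at Screening is an eligibility failure, and after Day 1 there is no further dose to withhold. Only an unscheduled or self-reported positive result between the two visits would bring it into play.

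What is at stake is the safety of a small group of subjects. The sample size, the endpoints and the analyses are not affected.

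**Working it through.** **Inputs**

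| Item | Value | Source |
|---|---|---|
| Screening window | Day -29 to Day 1 | 10.1 heading, Appendix I |
| Interval from Screening to Visit 2 | 0 to 29 days | 10.1 item 11 |
| Screening length | up to 30 days | Synopsis, duration of participation |
| Scheduled pregnancy tests | 1, at Screening | 10.1 item 8, Appendix I |
| Pregnancy tests among the Day 1 steps | 0 of 15 | 10.2 |
| ALA application | step 8 of Day 1, once only | 10.2, 8.4.1 |
| Planned subjects | 30, 10 per arm | 4.1 |

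**Step 1: the plan's own interval.** From Day -29 to Day 1 with no Day 0 is 1 - (-29) - 1 = 29 days, which agrees with item 11. Counting a Day 0 gives 1 - (-29) = 30 days, which agrees with the synopsis: 30 + 1 + 84 = 115 days on study.

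**Step 2: age of the result when ALA is applied.** This equals the interval from Screening to Visit 2:

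- combined visit: 0 days;
- separate visits: up to 29 days by item 11, or 30 by the synopsis.

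I have not added the general ±3-day visit window in section 10, because item 11 states its own range.

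**Step 3: does anything on Day 1 re-check the exclusion?** The steps before ALA are randomisation, vital signs, review of medications and adverse events, an abbreviated examination, the AK count, a skin assessment and curettage. None establishes pregnancy status. Other Screening measurements are repeated: vital signs, for instance, "will be performed after resting for 5 minutes at Screening and at day 1", and Appendix I marks concomitant medications and the AK count at both visits.

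**Step 4: how many subjects.** The documents do not give the share of women of childbearing potential. Assuming 0% to 20%:

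- 0.00 × 30 = 0 women;
- 0.20 × 30 = 6 women.

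Six is the ceiling under that assumption for women treated on an older result, and it requires all of them to have separate visits. It is not a count of pregnancies.

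**Step 5: after the change.** With the test on Day 1 before randomisation, the result is 0 days old in every case.

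**Step 6: why before randomisation.** Section 15.4 counts subjects in the ITT population from randomisation whether or not they are treated, and 12.3 does not replace withdrawals. A positive result found after step 1 of 10.2 could leave an untreated, unreplaced subject in an arm of 10, which is 1/10 = 10% of that arm.

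**The case against.** The strongest reply is that no rule in the protocol is broken. A Screening test does precede treatment, so the wording of 6.2 is satisfied. That is right, and it makes this a weakness of timing, not a contradiction. It does not remove the gap: the criterion can be met on paper while the excluded exposure takes place.

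The protocol also has other safeguards. Contraception is required, women planning a pregnancy are excluded, and the Day 1 review of medications and adverse events gives a woman who knows she is pregnant a chance to say so. These make a treated pregnancy unlikely. None of them verifies status on the day, and the protocol itself asks for a test in addition to contraception.

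The size is uncertain. The 0–20% share is an assumption, the split between combined and separate visits is unknown, and the documents give no estimate of fetal harm from one topical application. All of this stands, and it keeps the point modest.

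The comparison with other repeated measurements carries limited weight. The Day 1 AK count has its own purpose, because 15.4 defines baseline as the pre-dose Day 1 value.

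Two objections concern the remedy. First, moving the test means that a woman already pregnant at Screening is found later. That is a real cost, but nothing done at Screening puts her at risk. Second, 8.1 has a randomisation worksheet completed before Visit 1, which could seem to put randomisation ahead of any Day 1 test. Section 10.2 nevertheless makes randomisation by sequential envelope the first step of Visit 2, so a test can be read before it.

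**Conclusion.** The concern holds. With separate visits, the only scheduled pregnancy result can be up to 29 days old when ALA is applied (30 by the synopsis), and the protocol followed exactly could treat a woman whom 6.2 excludes. With a combined visit the problem does not arise.

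The likely number affected is small: 0 to 6 women treated on an older result if 0–20% of the 30 subjects are of childbearing potential and all of these have separate visits, with few if any pregnant. The change is worth making because it protects subjects at almost no cost.

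**What to change.** When the visits are separate, move the urine test from Screening to Day 1 and read it before randomisation, and so before ALA. The edits are:

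- **9.2.1:** state that the test is done on Day 1, before randomisation.
- **10.1 item 8:** do the test at Screening only when that visit is combined with Day 1.
- **10.2:** add the test as a new first step, ahead of randomisation.
- **Appendix I:** mark the test in the Day 1 column.
- **4.1:** base eligibility on the Screening data together with the Day 1 pregnancy result.
- **Terminology:** 9.2.1 and 10.1 define the tested group by childbearing age; use childbearing potential, as 6.2 already does.

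The cost is protocol wording only: no extra test and no extra visit. The drawback is that a positive result comes to light on Day 1, which wastes that treatment slot and the screening work-up. If the investigator prefers early detection, keeping the Screening test and repeating it on a separate Day 1 closes the same gap for one more urine test per woman concerned. Under either arrangement a urine test cannot detect very early conception, so the gap is narrowed and not eliminated.

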APPENDIX II. TREATMENT PROTOCOL

[figure not shown]
APPENDIX III. TIMING OF SYMPTOM ASSESSMENTS

Min	Symptom Assessment	Conventional Arm	Combination Arm	Daylight Arm
0		Begin 1 hour Incubation	Begin 15 minute incubation	Begin 15 minute incubation
5		Incubation	Incubation	Incubation
10		Incubation	Incubation	Incubation
15	X	Incubation	Sunscreen, BLU-U Exposure: 16m 40s	Sunscreen, Daylight Exposure: 60m
20		Incubation	BLU-U	Daylight
25		Incubation	BLU-U	Daylight
30	X	Incubation	End BLU-U, Begin Daylight Exposure: 60m	Daylight
35		Incubation	Daylight	Daylight
40		Incubation	Daylight	Daylight
45	X	Incubation	Daylight	Daylight
50		Incubation	Daylight	Daylight
55		Incubation	Daylight	Daylight
60	X	BLU-U Exposure: 16m 40s	Daylight	Daylight
65		BLU-U	Daylight	Daylight
70		BLU-U	Daylight	Daylight
75	X	End BLU-U, Sunscreen	End Daylight	End Daylight

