
TEST PRODUCT, DOSE, AND ROUTE OF ADMINISTRATION
	
Study medication—Aminolevulinic acid HCl topical solution 20% (Levulan Kerastick)
 
Study device—BLU-U blue light phototherapy illuminator
 
After preparation of the treatment area with acetone, one stick of Levulan (containing 354 mg ALA HCl) will be topically applied to the treatment area (face or scalp). Subjects will be randomized to one of three treatment arms to receive BLU-U exposure and/or daylight exposure. Treatment arms are as follows:
 
A. Conventional arm: Acetone preparation, ALA topical application, 1hour incubation, 16 minutes 40 seconds (16:40) BLU-U exposure, application of sunscreen.
 
B. Combination arm: Acetone preparation, ALA topical application, 15 minute incubation, 16:40 BLU-U exposure, application of sunscreen, 45 minute daylight exposure.
 
C. Daylight arm: Acetone preparation, ALA topical application, 15 minute incubation, application of sunscreen, 1 hour daylight exposure.

DURATION OF SUBJECT PARTICIPATION AND DURATION OF STUDY
	
Subjects will be on study for up to 115 days.
 
Screening: up to 30 days
 
Treatment: 1 day
 
Follow-up: 84 days
 
The total duration of the study is expected to be 16 months. Approximately 12 months for subject enrollment and 4 months for treatment and final subject follow-up.

CONCOMITANT MEDICATIONS	Allowed: Bland topical emollients such as Eucerin, Cetaphil. Prohibited: Any topical prescription medication on the treatment area during the study.
EVALUATIONS	
PRIMARY ENDPOINT	Primary objective is to determine whether daylight PDT affords a reduction in treatment symptoms of pain, stinging/burning, and itching/pruritus. Primary endpoints will be: 1) peak symptom level and composite score during the treatment period 2) symptom level and composite score at the end of treatment exposure.
SECONDARY ENDPOINTS	1) To determine efficacy in clearance of AK at 12 weeks: A. percent reduction in number of AKs from baseline to 12 weeks B. proportion of subjects with complete and partial clearance of AKs as described above 2) To determine whether daylight PDT affords, at end of treatment, a reduction in composite local skin reaction 3) To determine whether daylight PDT has a faster resolution of composite treatment symptoms and local skin response during days 8, 29, and 84.

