8.4.1 Dosage/Dosage Regimen

Aminolevulinic acid HCl topical solution 20% (Levulan Kerastick) will be applied topically once by a healthcare provider on the day of treatment. One Levulan Kerastick will be applied to the treatment area on the face or scalp. Care will be taken to avoid the eyes and mouth.

Treatment arms are as follows:

- A. Conventional arm:** Acetone preparation, ALA topical application, 1 hour incubation, 16:40 BLU-U exposure, application of sunscreen.
- B. Combination arm:** Acetone preparation, ALA topical application, 15 minute incubation, 16:40 BLU-U exposure, application of sunscreen, 45 minute daylight exposure.
- C. Daylight arm:** Acetone preparation, ALA topical application, 15 minute incubation, application of sunscreen, 1 hour daylight exposure.

Due to photosensitivity, subjects should avoid sunlight, tanning beds, and any prolonged or intense light exposure for 40 hours after application of ALA HCl, outside of the assigned treatment regimen. Subjects should not wash or clean their faces until all steps of treatment have been completed.

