8.4.3 Administration Instructions

Aminolevulinic acid HCl 20% topical solution (Levulan Kerastick) will be applied topically once by the study provider. After acetone preparation of the treatment area,

Levulan Kerastick will be applied to the subject's affected areas within the treatment area. The treatment area will be either the face or scalp; the site will be determined at Screening. Prior to Levulan treatment, any hypertrophic AKs in the treatment area will be scraped with a curette by the study provider to remove thick scale.

The study provider will prepare and administer Levulan Kerastick in the following manner:

1. Hold Levulan Kerastick so the applicator cap is pointing up.
2. Crush bottom ampule containing solution vehicle by applying finger pressure to marked location on the cardboard sleeve.
3. Crush the top ampule containing the ALA HCl powder by applying finger pressure to marked location on the cardboard sleeve. To ensure both ampules are crushed, continue crushing the applicator downward.
4. Holding the Levulan Kerastick between the thumb and forefinger, pointing the applicator cap away from the face, shake the Levulan Kerastick gently for at least 30 seconds to mix ALA HCl and solution vehicle. Do not press on end cap while shaking.
5. Apply contents of one Levulan Kerastick using applicator tip to all affected areas within treatment area. Mouth, periorbital area, and all mucosal surfaces will be avoided.

Depending on the assigned treatment arm, patients will receive 16 minutes, 40 seconds of artificial blue light on the treatment area via BLU-U blue light phototherapy illuminator and/or daylight exposure for the assigned duration. Light exposure will be provided by the unblinded study provider.

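### Appendix III contradicts the written combination-arm regimen: sunscreen comes before the blue light instead of after it, and daylight is labelled 60 minutes instead of 45

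*Combined protocol and SAP*

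**What the plan says.** The synopsis, section 4.1 and section 8.4.1 describe arm B identically: "15 minute incubation, 16:40 BLU-U exposure, application of sunscreen, 45 minute daylight exposure". For the conventional arm (A), section 8.4.1 gives "1 hour incubation, 16:40 BLU-U exposure, application of sunscreen". In the daylight arm (C), sunscreen follows the 15-minute incubation and precedes one hour of daylight.

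Appendix III lays out the treatment day in 5-minute rows, one column per arm. Its four relevant cells are:

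- Arm B, minute 15: "Sunscreen, BLU-U Exposure: 16m 40s"
- Arm B, minute 30: "End BLU-U, Begin Daylight Exposure: 60m"
- Arm C, minute 15: "Sunscreen, Daylight Exposure: 60m"
- Arm A, minute 75: "End BLU-U, Sunscreen"

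The minute-75 row ends daylight in arms B and C.

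Two other places describe the treatment day without placing the sunscreen step. Section 8.4.3 refers only to BLU-U and/or "daylight exposure for the assigned duration". The Day 1 steps in section 10.2 say "Light exposure (BLU-U and/or sunlight, depending on treatment arm".

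**The concern.** Appendix III and the regimen text give arm B a different order of steps and a different daylight duration. The order matters more. If staff worked from the minute-15 cell, arm B would have its blue light delivered through sunscreen, while arm A receives sunscreen only after BLU-U. Any screening effect of the product would then be mixed into the comparison of A with B on symptoms (section 15.3) and on AK clearance (section 15.4). Section 15.3 compares all three arms, so B with C would be touched as well; A with C would not. Staff obeying the appendix would also be departing from section 8.4.1, and section 13 counts non-compliance with the assigned arm's regimen as a protocol violation.

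The daylight label matters only if it overrides the table's final row. In that case arm B would still be under exposure at the last scheduled symptom score, and the primary endpoint of symptoms at the end of exposure would have no scheduled measurement in that arm.

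**Working it through.** **Sunscreen order.** Setting the table against the text, arm by arm:

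| Arm | Regimen text | Appendix III | Agree? |
|---|---|---|---|
| A | after BLU-U | minute 75, as BLU-U ends | yes |
| B | after BLU-U, before daylight | minute 15, before BLU-U; none at minute 30 | no |
| C | after incubation, before daylight | minute 15, before daylight | yes |

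Two of the table's three sunscreen cells match the text. For arm B, all three regimen statements (synopsis, 4.1, 8.4.1) disagree with the one table cell. The matching entries for arms A and C make a text-extraction fault unlikely.

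**Daylight duration.** Inputs: arm B daylight starts at minute 30 and ends at minute 75 (Appendix III); the label is 60 minutes (Appendix III); the text gives 45 minutes; the last symptom score is at minute 75 (section 9.1.8).

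- From the table's rows: 75 − 30 = 45 minutes, which agrees with the text and not with the label.
- From the label on the same grid: 30 + 60 = minute 90, and 90 − 75 = 15 minutes past the last row.

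Using the exact BLU-U time of 16:40 instead of the 5-minute grid:

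- Arm A: 60:00 + 16:40 = 76:40.
- Arm B with 45 minutes of daylight: 15:00 + 16:40 + 45:00 = 76:40, the same as arm A.
- Arm B with 60 minutes of daylight: 15:00 + 16:40 + 60:00 = 91:40, which is 91:40 − 75:00 = 16:40 after the last score.
- Arm C: 15:00 + 60:00 = 75:00.

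These totals allow no time for applying sunscreen. With 45 minutes, arm B fits the table apart from 1:40 of rounding that arm A shares. With 60 minutes it does not fit. The label is therefore wrong, and 45 minutes is what was meant.

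**Likely origin.** Sunscreen straight after a 15-minute incubation and a 60-minute daylight period are both features of arm C's minute-15 cell. A copying error from that column would explain both arm B entries. This is inference.

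**The case against.** The strongest reply is that the plan already settles the regimen. Three statements agree, one of them in the section headed as the dosage regimen, and section 13 ties violations to the regimen as described for the arm. Appendix III is titled as a schedule of symptom assessments, and its assessment times are correct. Appendix II, the treatment protocol, is a figure that is not reproduced here and may show the right order. The effect on outcomes is also unproven: nothing in the documents says that the sunscreen weakens BLU-U light, and by design all of arm C's light and all of arm B's daylight arrive after sunscreen. On this view the point is editorial.

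Much of that stands. The intended order is clear, the harm depends on staff following the wrong cell, no effect size can be given, and the 60-minute label does nothing if the final row is followed.

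It does not make the sunscreen cell harmless. Appendix III goes beyond assessment times and schedules treatment steps by the minute. Neither section 10.2 nor section 8.4.3 places the sunscreen step, so neither would correct a reader of the table. Under section 8.2 the unblinded coordinator handles both light exposure and symptom scoring, so the person timing the scores has reason to have this table in hand. That the design accepts sunscreen before daylight does not show that it accepts sunscreen before BLU-U; the regimen text puts it after BLU-U in both arms that receive BLU-U.

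**Conclusion.** The concern holds and should be fixed. Two cells in the arm B column of Appendix III contradict the written regimen, affecting one arm of three (10 of 30 planned subjects). The sunscreen cell is a conflict in the order of treatment steps; the 60-minute figure is a labelling error contradicted by the table's own 45-minute span.

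This rests on taking the three agreeing regimen statements as the intended regimen. Nothing in the documents shows that any subject was treated in the wrong order. The size of any resulting bias cannot be estimated, because the sunscreen is not described. Appendix II could not be checked. The design, sample size and planned analyses are not in question.

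**What to change.** Before the first arm B treatment, correct two arm B cells in Appendix III:

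- Minute 15: drop sunscreen, leaving only the start of the 16:40 BLU-U exposure.
- Minute 30: list the end of BLU-U, then sunscreen, then the start of 45 minutes of daylight.

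Check that the Appendix II figure shows the same sequence. The corrected cells keep the table's 5-minute rounding (exact end 76:40 against row 75), which a short footnote could state.

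The cost is a minor amendment submitted to the IRB under sections 17.1 and 17.2. Section 17.2 lets purely logistical or administrative changes proceed without prior approval. Aligning a table with the approved regimen may qualify, but because a treatment step is involved, it is safer to obtain approval first.
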